## Statistical Analysis Plan

---

- Receive the incorrect study medication throughout the study

Subjects will be included in their 'as treated' treatment group. Note that this will be the same as the randomized treatment because receiving the wrong study medication is a major deviation.

Data listings, including protocol deviations (Section 5.9), will be provided to identify subjects to be excluded from the PP population prior to database lock. Precise reasons for excluding subjects will be documented prior to locking the database.

### **5.7. PHARMACOKINETIC (PK) POPULATION**

The PK population will include all subjects in the safety population who have at least one quantifiable concentration of APL-2 (even if <LLOQ).

### **5.8. PHARMACODYNAMIC (PD) POPULATION**

The PD population will include all subjects in the safety population who have at least one quantifiable post dose PD parameter.

### **5.9. PROTOCOL DEVIATIONS**

All protocol deviations will be reviewed and documented before database lock. Protocol deviations will be recorded by the site staff, study monitors and medical monitor reviewers. They may also be identified through programmable checks of the data.

Key protocol deviations include:

- Violations of inclusion and exclusion criteria. This includes unknown violations at enrolment and on-study violations, like taking a prohibited medication
- Receive the incorrect study medication

Protocol deviations will be categorized as either major or minor prior to database lock. All protocol deviations will be listed.

### **5.10. DATA REVIEW FOR ANALYSIS POPULATIONS**

After all the data has been entered and verified in the database, a review will be performed to define the analysis populations. The review will also check the quality of the data, identify outliers and make decisions on how to deal with problems in any data (e.g. missing values, withdrawals, protocol deviations). After the pre-analysis review, resolution of all issues and documentation of all decisions the database will be locked.

## Statistical Analysis Plan

---

### 6. GENERAL ASPECTS FOR STATISTICAL ANALYSIS

#### 6.1. GENERAL METHODS

All statistical tests will be 2-sided at the 0.1 level of significance. To understand the clinical significance of the estimated treatment effects and to aid interpretation of the formal hypothesis testing 2-sided 95% CI will also be provided. There will not be any adjustments for multiple comparisons.

For all independent ophthalmic assessments (performed by DARC laboratory), if assessments by only two independent readers are available, then the mean of the 2 readings will be used in the calculation of summary statistics. If assessments by three independent readers are available, then the median of the three readings will be used for the summary calculations.

Continuous variables will be summarized using the number of non-missing observations (n), mean, standard deviation (SD), median, minimum, and maximum. Geometric mean and coefficient of variation (CV) will be included for PK parameters, where appropriate. Categorical variables will be summarized using frequencies and percentages. Unless stated otherwise, for all percentages, the number of subjects in the analysis population for the treatment group will be the denominator.

Unless otherwise specified, the estimated mean and median for a set of values should be printed out to 1 more decimal place than the original values, and standard deviations should be printed out to 2 more decimal places than the original values. The minimum and maximum should report the same number of decimal places as the original values. Percentages will be displayed with 1 decimal place; except percentages will not be presented when the count is zero and 100% will be presented as an integer.

Unless stated otherwise, baseline will be taken as the last available non-missing assessment prior to first study drug administration.

Subjects can discontinue treatment but remain in the study for follow-up. All assessments will be included in summary tables or analyses unless stated otherwise.

For all summary tables, data will be presented by treatment group and by pooled sham and pooled APL-2. For summaries by-visit pooled sham and pooled APL-2 will only be presented for the bi-monthly visits. The treatment group labels for summary tables will be:

- APL-2 Monthly
- APL-2 EOM
- APL-2 Pooled
- Sham Monthly
- Sham EOM
- Sham Pooled

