## Statistical Analysis Plan

---

0.2mm/year and a 2-sided test at the 10% level of significance.

Assuming a 15-20% loss to follow-up, a total sample size of 240 subjects (AM=80, AEOM=80, SM=40 and SEOM=40) will be required to obtain 201 evaluable subjects (i.e. subjects who complete the study).

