## Statistical Analysis Plan

---

with the last available pre-injection IOP value at previous visits. Missing post-injection values will not be imputed.

Values  $\geq 30$  mmHg will also be identified. Missing IOP values will not be imputed for this indicator endpoint.

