### **5.3. SAFETY POPULATION**

The safety population will include all subjects randomized who receive at least one injection of study medication. The safety population summary groups will be based on the actual treatment received for the whole duration of the study. The grouping rule for subjects who receive study medication from the incorrect injection during the study will be decided on a case by case basis before database lock. This population will be used for all safety analyses.

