### **11.2. INTRA OCULAR PRESSURE (IOP)**

The observed and change from baseline values in IOP over time will be summarized by treatment group and protocol specified time points for the safety population. Summaries will present the descriptive statistics for baseline and change from baseline data. The acute change in IOP after each injection (i.e., change from pre-injection to post-injection value) will also be summarized at each protocol specified time point.

The number of subjects with IOP  $\geq 30$  mmHg post injection will be summarized by treatment group, visit and over the whole study.

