### **11.3. ANTERIOR SEGMENT EXAMINATION**

Anterior segment examination endpoints (abnormal reaction to light, active inflammation present in cornea, abnormal anterior chamber, any opacity in lens, aqueous reaction flare and aqueous reaction cells) will be summarized separately for the study eye and the fellow eye by treatment group and protocol specified time points for the MITT population, using summary statistics for categorical variables.

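### By-visit categorical safety percentages are divided by the whole analysis population, so they understate the risk among subjects assessed by the share of the arm not assessed at that visit

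*SAP*

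**What the plan says.** SAP 6.1 has categorical variables summarized as frequencies and percentages, and fixes the denominator: unless stated otherwise, "for all percentages, the number of subjects in the analysis population for the treatment group will be the denominator". For most safety tables that population is set by SAP 5.3: "The safety population will include all subjects randomized who receive at least one injection of study medication". Membership depends on a first injection, so the number does not fall as subjects leave.

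The by-visit categorical safety summaries are specified as follows.

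- **SAP 11.2, IOP:** the number of subjects at or above 30 "mmHg post injection will be summarized by treatment group, visit and over the whole study". SAP 4.3.2 adds: "Missing IOP values will not be imputed for this indicator endpoint".
- **SAP 11.3, anterior segment:** summarized by "protocol specified time points for the MITT population, using summary statistics for categorical variables". SAP 11.4 treats the posterior segment in the same way.
- **SAP 11.6, urinalysis:** categorical results by treatment group and time point.

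None of these states a different denominator. The only one stated in the safety sections is for LOCS III (SAP 11.5): phakic subjects with an assessment at any time in the study, which is not visit-specific. Hematology and chemistry shift tables (11.6) carry a missing category; the summaries listed above specify none. Continuous variables are reported with the number of non-missing observations (6.1).

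**The concern.** At a given visit some of the arm has no assessment. A subject who has withdrawn, or who misses the visit, has no examination or urine sample. A subject who has stopped injections but stays in the study is examined, but has no post-injection pressure. Under the default rule all of them remain in the denominator of the tables they are missing from.

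Two things are at stake. First, a constant risk per assessed subject would appear to decline over the year simply because fewer subjects are assessed. Second, if one schedule were stopped more often than another, its by-visit percentages would be lowered more. Increase in IOP, ocular inflammation, vitreous hemorrhage and retinal detachment or tear are secondary safety endpoints in the Protocol Synopsis, and the trial compares a monthly with an every-other-month schedule, so readers will look at these tables side by side.

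The SAP also treats related quantities differently within one section. In 11.2 the mean acute pressure change rests on subjects with readings, while the percentage at or above 30 mmHg rests on everyone ever injected.

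**Working it through.** **Inputs from the documents**

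- Planned arm sizes: AM 80, AEOM 80, SM 40, SEOM 40, total 240 (SAP 3.3).
- Planned loss: "Assuming a 15-20% loss to follow-up" (SAP 3.3); Protocol 11.3.4 uses 83.5% retained. Protocol 11.3 ties the calculation to the 12-month per-protocol analysis.
- Stopping rates by arm: none given. Event rates for these tables: none given.

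**The plan's own figure.** Required N = evaluable / share retained = 201 / 0.835 = 240.7, against 240 stated, so it reproduces. Conversely 201/240 = 83.75% retained, that is 16.25% lost.

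**Formula.** Let N be the population of the arm, m the number assessed at the visit and p the risk among those assessed. The expected numerator is p × m, so

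printed percentage = p × m / N = p × (1 − d), with d = 1 − m/N.

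The relative understatement is d, whatever p is.

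**One arm, p = 10% (assumed for illustration)**

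| Share not assessed, d | Printed |
|---|---|
| 15% | 10% × 0.85 = 8.5% |
| 16.25% (201 of 240 retained) | 10% × 0.8375 = 8.4% |
| 20% | 10% × 0.80 = 8.0% |

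**In counts: arm of 80, 6 subjects with post-injection IOP of 30 mmHg or more (6 is assumed).** The planned rule gives 6/80 = 7.5%. Among those assessed:

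- 68 assessed (15% missing): 6/68 = 8.8%
- 67 assessed (the planned evaluable number per group): 6/67 = 9.0%
- 64 assessed (20% missing): 6/64 = 9.4%

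**Between arms, same p = 10% in both (all shares assumed)**

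| Not assessed | Printed | Ratio |
|---|---|---|
| 15% and 15% | 8.5% and 8.5% | 1.00 |
| 20% and 15% | 8.0% and 8.5% | 0.94 |
| 30% and 15% | 7.0% and 8.5% | 0.82 |

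Equal loss lowers both percentages and leaves their ratio unchanged.

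**Which subjects count towards d**

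| Subject | Post-injection IOP (11.2) | Segment examinations (11.3, 11.4), urinalysis (11.6) |
|---|---|---|
| Withdrawn, or missed the visit | not assessed | not assessed |
| Stopped injections, attends visits | not assessed | assessed |

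The second row follows from Protocol 10.5.1 and SAP 3.2, which let subjects who stop treatment continue scheduled procedures, and from SAP 6.1, which includes their assessments. The every-other-month schedule adds nothing to d, because SAP 6.3 leaves odd-month visits in those groups unsummarized.

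**The case against.** The strongest case against has five parts.

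1. **The information is available elsewhere.** SAP 7.1 plans attendance and injection counts by visit, 7.6 plans the number injected at each month, and the n for acute IOP change in 11.2 is close to the number with a post-injection reading. This stands in part: a reader could rebuild most denominators, but the printed percentages would remain as they are, and attendance is not the same as a non-missing reading.
2. **The main safety conclusions lie elsewhere.** The primary safety endpoints are TEAEs and AESIs (SAP 4.3.1), counted per subject over the study, where the full population is right. IOP of 30 mmHg or more is also summarized over the whole study. This stands: the affected tables are descriptive and carry no test.
3. **Assessed subjects are a selected group.** If subjects leave because of pressure or inflammation, dividing by those who remain can also flatter a poorly tolerated schedule. This stands, and is why a count of subjects not assessed must accompany the percentage.
4. **The table shells are separate documents and may set denominators.** They may; they were not available for this review. The SAP text sets a rule, and nothing in it exempts these tables.
5. **Where all grades are tabulated, counts will fall short of N and the gap will show.** True for graded findings, but the percentage in each grade is still divided by N.

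Three stronger readings are tempting and are not supported. A reader might infer that absent subjects are scored as event-free. No rule says so: missing IOP is not imputed for the indicator, and SAP 4.3.3 sets missing flare or cells to 0 only when the anterior chamber was recorded as normal. A reader might infer that stopping injections dilutes every by-visit safety table; it dilutes only post-injection IOP. And a reader might infer that the less tolerated schedule will look safer. Protocol 11.5 does contemplate fewer active-arm subjects completing, but no document gives a rate by arm.

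**Conclusion.** The point holds for by-visit categorical safety percentages in SAP 11.2 (post-injection IOP of 30 mmHg or more), 11.3, 11.4 and 11.6 (categorical urinalysis). Following the SAP as written, each prints below the risk among those assessed by the share of the arm not assessed at that visit.

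The size rests on a planning figure, not on observed loss. If 15-20% were missing by Month 12, the relative understatement there would be 15-20%; with loss accumulating over time it would be smaller at earlier visits. For post-injection IOP, subjects who stop injections but remain in the study add to the share. Any distortion between arms depends on unequal stopping, which is an assumption in the examples above.

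Whole-study incidences of TEAEs, AESIs and IOP of 30 mmHg or more are not affected, nor are sample size and power. This is worth correcting because the remedy is simple, but it does not threaten the primary safety analysis.

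**What to change.** Amend SAP 6.1 with an exception to the default:

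- For by-visit categorical safety summaries, the denominator is the number of subjects with a non-missing assessment at that visit.
- For post-injection IOP, it is the number injected (or sham-injected) at that visit with a post-injection reading.
- Print that n and a count of subjects not assessed, per arm and visit.
- Keep the population N for whole-study incidence and for disposition.

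While editing, reconcile the base population: SAP 11 puts all safety evaluation on the safety population, but 11.3 and 11.4 name MITT. The count of subjects not assessed needs one agreed starting number.

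The cost is a short SAP amendment and a denominator change in the table programs; no new data are needed. Some percentages become slightly less favourable. Percentages among assessed subjects still describe only those who remain, and the accompanying count makes that visible without removing it.

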## Statistical Analysis Plan

---

In general, all summary tables will display the treatment groups in the above order except for cases where it's more convenient for comparison purposes to layout the Sham Pooled group with both AMP-2 Monthly and APL2- EOM groups on the same page. In by-visit summary tables the baseline will be summarized using all available data, but also for each visit using only the baseline data from subjects with available data at the visit.

All data will be listed. Data listings will be presented by treatment group. Data listings will present study days in addition to dates, where study day is derived as (assessment date – first day of dosing) +1. The first day of dosing will be identified as Study Day 1. The analysis visit (derived from visit windowing – refer to Section 6.3) alongside the actual visit and the time since last dose will also be included in relevant listings.

All statistical analyses will be performed using SAS® (Version 9.4 or higher, SAS Institute Inc., Cary, NC, USA).

### **6.2. MISSING DATA**

All possible efforts will be made to minimize missing data. As missing data may potentially bias the outcome of the statistical analyses and the subsequent estimation of the magnitude of the treatment effect, different strategies will be applied to provide a balanced assessment of treatment efficacy.

Where specified screen values or pre-dose unscheduled measurements may be used as a baseline value in the event of missing Day 1 measurements.

Handling of missing dates/times for the start/stop of medications and adverse events are detailed in Sections 7.5 and 11.1 respectively.

The original data will always be presented in the listings.

#### **6.2.1. Efficacy Data**

Missing data may result from a subject discontinuing, a particular assessment missed at a visit or a complete visit missed. For the primary analysis sensitivity analyses will be conducted to assess the influence of missing data. These include:

- Last observation carried forward (LOCF). The LOCF approach will replace missing Month 12 (or Month 18) data with the last observation recorded.
- Linear mixed effects model for repeated measures (MMRM). The MMRM approach assumes data are missing at random and uses a restricted maximum likelihood (REML) repeated measures model to analyse available data.

## Statistical Analysis Plan

---

### 6.2.2. Pharmacokinetic and Pharmacodynamic Data

APL-2 concentrations reported as below the limit of quantification (BLQ) will be taken as zero for linear plots, and equal to the lower limit of quantification (LLOQ) for semi-logarithmic plots. For the computation of descriptive statistics, BLQ will be taken as zero, except for the calculation of the geometric mean where the LLOQ will be used.

If a BLQ value falls between two quantifiable concentrations the value will be set equal to the LLOQ, unless its exclusion can be justified (e.g. implausibility given the profile observed and known PK properties).

If a baseline PD value is zero, then the percentage change from baseline will not be calculated. If a PD value is BLQ then the value will be set to the LLOQ. Similarly, for the PD plots, a BLQ value will be set equal to LLOQ.

### 6.3. VISIT WINDOWS

Analysis visits will be derived with windowing for the Day 7 and monthly visits. Screening can be up to 2 weeks before start of study treatment. Baseline is defined as the date of randomization. Table 2 below defines the analysis windows for the visits. If 2 or more treatment visits occur within a window, the closest visit to the target day will be used as that analysis visit; if 2 visits are equidistant from the scheduled analysis visit day, the later analysis visit will be used.

Visit windowing will be reviewed prior to reporting and assessments where the actual study day does not fall within the protocol visit window for the Day 7 or monthly visits will be identified and the allocation reviewed. For the two EOM treatment groups, visits that lie within the window for an odd month will not be summarized.

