8.3.4 Injection Visits – Monthly or EOM until month 12 -

Monthly Groups: Days 30, 60, 90, 120, 150, 180, 210, 240, 270, 300, 330 and 360 - Visits 4, 5, 6, 7, 8, 9, 10, 11, 12, 13, 14 and 15, respectively.

EOM Groups: Days 60, 120, 180, 240, 300 and 360 – Visits 4, 5, 6, 7, 8 and 9 respectively.

Unless specified, all ophthalmic procedures (including imaging) are to be performed on the **study eye only**. The following procedures will be performed at all injection visits:

1. Obtain information on any changes in medical health and/or the use of concomitant medications.
2. Collect vital signs pre- and post-dose. Vital signs will be measured within approximately 1 hour prior to dosing for the pre-dose time point. Post-dose vital signs readings will be performed within 30 minutes after dosing.
3. Collect blood for PK analysis.
4. Perform urine pregnancy test before APL-2 injection. **-WOCBP only-**
5. Perform BCVA. **-Both eyes on Day 360 only-**
6. Perform LL-BCVA. **-Both eyes on Day 360 only-**
7. Perform a complete ophthalmic exam including slit-lamp exam of the cornea, iris, anterior chamber, lens (LOCS III if any opacity on the lens noted) and aqueous reaction (cells and flare), dilated fundus exam of the vitreous and retina and IOP measurement.
8. Perform the IVT injection of APL-2 (or Sham injection) as described in the MOP.
9. Monitor the study eye within 15 minutes post-injection as outlined in [Section 9.8](#) and in the MOP.
10. Monitor for adverse events.

The following procedures will be performed only at specific visits, as noted:

1. Collect blood and urine for laboratory analysis and forward the samples to the central laboratory. - **Only on Days 60, 180 and 360 for all groups -**
2. Collect blood for genetic marker analysis (if applicable, see [Section 9.3](#)) and forward the samples to the central laboratory. - **Only on Days 60 for all groups -**
3. Perform SD-OCT imaging and forward the images to the CRC. - **Only on Days 60, 180 and 360 for all groups -**
4. Perform FAF imaging **of both eyes** and forward the images to the CRC. - **Only on Days 60, 180 and 360 for all groups -**
5. Perform IR imaging (if applicable) **of both eyes** and forward the images to the CRC. - **Only on Days 60, 180 and 360 for all groups -**

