8.3.5 Follow up visit - Day 450 -

Visit 16 and 10 for Monthly and EOM, respectively

Unless specified, all ophthalmic procedures are to be performed on the **study eye only**.

1. Obtain information on any changes in medical health and/or the use of concomitant medications.
2. Collect blood for PK analysis.
3. Collect vital signs.
4. Perform urine pregnancy test. **-WOCBP only-**
5. Perform BCVA.
6. Perform LL-BCVA.
7. Perform a complete ophthalmic exam including slit-lamp exam of the cornea, iris, anterior chamber, lens (LOCS III if any opacity on the lens noted) and aqueous reaction (cells and flare), dilated fundus exam of the vitreous and retina and IOP measurement.
8. Monitor for adverse events.

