## Statistical Analysis Plan

---

Subjects diagnosed with GA associated with AMD in the study eye and who meet all inclusion/exclusion criteria will be included in the study. The study will randomize approximately 240 subjects across 40 multinational sites to obtain at least 200 subjects who complete the study.

Subjects should be screened 14 ( $\pm 5$ ) days before receiving APL-2. Subjects who meet all inclusion and exclusion criteria and are confirmed as eligible by the Central Reader Centre (CRC) will return to the clinic for the randomization visit (Day 1). At this visit, subjects will be randomized in a 2:2:1:1 manner to receive APL-2 Monthly (AM), APL-2 Every-Other-Month (AEOM), Sham injection Monthly (SM) or Sham injection Every-Other-Month (SEOM), respectively.

All subjects will return to the clinical site on Day 7 to assess acute safety after the first injection. After that, subjects in the monthly groups will return to the clinical site for additional APL-2 (or Sham) injections and study procedures every month until Month 12. Subjects in the EOM groups will return to the clinical site for additional APL-2 (or Sham) injections and study procedures every two months until Month 12. All subjects will return for follow-up visits 3 and 6 months after Month 12 (Months 15 and 18, respectively).

Subjects who discontinue study treatment, can continue participation in the study and return to the clinical site for their scheduled study procedures (with the exception of APL-2/Sham administration). Subjects who fully withdraw from the study before Month 12, should complete the Termination Visit.

Safety will be assessed throughout the study; serial blood samples and urine samples will be collected. Blood samples will also be collected for the PK assessment of APL-2.

An external, independent Safety Monitoring Committee (SMC) will review cumulative unmasked safety data and will have the responsibility to conduct a thorough safety assessment after the first 20 subjects have completed the Day 7, Month 2 and Month 6 visits. A key responsibility of the SMC will be to make a recommendation whether to continue, modify or stop the study based upon an evaluation of emerging safety data, in particular Adverse Events of Special Interest (AESI outlined in Protocol Section 10.1.3). Additional regular or ad-hoc safety reviews will be scheduled as recommended by the SMC.

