### **8. EFFICACY**

For the primary 12-month analyses, all efficacy data up to Month 12 will be included. For the final 18-month database lock, all by-visit summaries and analyses of change from baseline over time that are specified in this section, whenever applicable, will be repeated to include all data up to Month 18. The summary or analysis of data at Month 12 will be repeated for the data at Month 18.

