#### **8.1. PRIMARY EFFICACY ENDPOINT AND ANALYSIS**

The primary endpoint is the change from baseline in square root area for GA lesion at Month 12 as measured by FAF. Baseline will be taken as the last available non-missing assessment prior to first study drug administration, this should be the screening assessment for the primary endpoint.

The change from baseline in square root area for GA lesion at Month 2, 6 and 12 will be analysed for the MITT population with a MMRM. The model will include the fixed effects of treatment (3 groups: AM, AEOM and Sham), baseline square root area for GA lesion, visit (2, 6 and 12 months), treatment by visit interaction, visit by baseline interaction and treatment by baseline interaction. An unstructured covariance structure will be used to model the within subject error. The Kenward-Rogers approximation will be used to estimate the denominator degrees of freedom. If the treatment by baseline interaction is not significant at the 10% level then this term will be removed from the model. If significant at the 10% level results will be presented both including and excluding this term and the nature of the interaction will be investigated before deciding on an approach for presenting results that include the treatment by baseline interaction.

All available data will be included in the analysis. The analysis model table will be presented. The treatment comparisons (AM vs Sham, AEOM vs Sham and AM vs AEOM) at Months 2, 6 and 12 will also be presented with the estimate, standard error and 95% CI. If the treatment effect is significant at the 10% level then the treatment means will be compared using the least significant difference (LSD) method and the p-value presented. In addition, the estimated mean (i.e. Least-Squares mean) change from baseline in square root area for GA lesion with  $\pm$  SE of mean change, will be plotted over time by treatment group.

The model assumptions will be checked by evaluating the model residuals. A Shapiro-Wilks test will

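### Read literally, the SAP's odd-month rule drops both every-other-month arms from the scheduled Month 15 summaries, and Table 2 has no rule for visits that fall between windows

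*SAP*

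**What the plan says.** SAP 6.3 assigns visits to analysis windows and then sets a special rule for the EOM arms: "For the two EOM treatment groups, visits that lie within the window for an odd month will not be summarized". The sentence has no upper limit and no exception. Table 2 runs past the treatment period and gives these late windows in Study Days: Month 12, 347 to 376; Month 15, 412 to 481; Month 18, 511 to 571.

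Month 15 is a scheduled visit for everyone. SAP 3.2 says: "All subjects will return for follow-up visits 3 and 6 months after Month 12 (Months 15 and 18, respectively". Protocol 8.3.5 numbers it for each schedule: "Visit 16 and 10 for Monthly and EOM, respectively". That section and the flow charts list BCVA, LL-BCVA, the eye examination with IOP, vital signs, and blood for drug concentration and antibodies at this visit.

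SAP section 8 says that for the 18-month lock the by-visit summaries "will be repeated to include all data up to Month 18", and the rationale for V3.0 says the same. SAP 9.1, 11.2 to 11.4, 11.7 and 11.8 call for summaries at the time points the protocol specifies, of which Month 15 is one. SAP 6.1 shows pooled sham and pooled APL-2 in by-visit tables only at bi-monthly visits.

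For Day 7 or monthly assessments outside the protocol window, SAP 6.3 says only that they "will be identified and the allocation reviewed". On the primary analysis, SAP 8.1 says: "All available data will be included in the analysis".

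**The concern.** The odd-month rule makes sense for Months 1 to 11, when the EOM arms have no scheduled odd-month visit and a stray attendance would give a table cell with a handful of subjects. Month 15 is different. It is odd, it has a window, and the EOM arms are due then. A programmer who follows the sentence as written would leave AEOM and SEOM blank at Month 15.

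Month 15 is also the first scheduled visit after the last injection at Month 12, so it is where the two regimens can first be set side by side off drug. Without the EOM arms, the table would show APL-2 monthly beside sham monthly and nothing else.

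The gaps in Table 2 are a separate weakness. The MMRM in SAP 8.1 needs each image labelled Month 2, 6 or 12. An image taken on a day outside all windows has no label, and the SAP gives no rule for assigning one. Protocol 7.2 and SAP 3.4 leave sponsor and CRO personnel unmasked, so case-by-case placement of a primary-endpoint image is better avoided.

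**Working it through.** **1. Reproduce Table 2.** For Month m from 1 to 12 the target is 30m + 1 and the window is target −14 to target +15. For m = 12 this gives 361 and 347 to 376, as printed. Month 18 is 541 ± 30 = 511 to 571, as printed. The Month 15 upper limit is 451 + 30 = 481, as printed. The lower limit does not reproduce: 451 − 30 = 421, but the table has 412. This may be a transposition, which is an inference only.

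**2. Does the EOM Month 15 visit fall under the rule?** The protocol visit is Day 450 ± 14, which is Study Day 451 ± 14 = 437 to 465 in the SAP's numbering. That range lies wholly inside 412 to 481, so every on-time EOM Month 15 visit is in an odd-month window.

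**3. How many subjects?** SAP 3.3 plans "AM=80, AEOM=80, SM=40 and SEOM=40".
- EOM arms: 80 + 40 = 120 of 240. From the ratio, (2 + 1)/(2 + 2 + 1 + 1) = 50%.
- With the plan's assumed 15-20% loss to follow-up: 120 × 0.85 = 102 down to 120 × 0.80 = 96.
- Left at Month 15 as planned: AM 80 and SM 40. Pooled sham would be 40 + 40 = 80, but SAP 6.1 already withholds that column because Month 15 is not on the two-month grid.

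**4. Is the primary endpoint involved?** Protocol 8.3.4 schedules on-treatment FAF "Only on Days 60, 180 and 360 for all groups", and the flow charts add only screening and Day 540. There is none at Day 450, so the odd-month rule at Month 15 removes no lesion measurement.

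**5. The gaps.**
- Between Months 12 and 15: Days 377 to 411, 411 − 377 + 1 = 35 days.
- Between Months 15 and 18: Days 482 to 510, 510 − 482 + 1 = 29 days.
- A Month 12 visit in the first gap is 377 − 361 = 16 to 411 − 361 = 50 days late.
- Visits inside the protocol windows (Month 12: 355 to 367; Month 15: 437 to 465; Month 18: 527 to 555) are all covered.
- If 412 was meant to be 421, the first gap is Days 377 to 420, or 44 days.

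**6. What would simply widening Month 12 do?** Protocol 11.3.1 assumes untreated growth of 0.33 mm/year. An image 50 days late carries 0.33 × 50/365 = 0.045 mm of extra growth. The design difference in protocol 11.3.3 is 0.33 − 0.23 = 0.10 mm, so the extra growth in that one subject is about 45% of it.

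**The case against.** The strongest reply is that the SAP as a whole points the other way. SAP 6.3 opens by describing windows for Day 7 and the monthly visits, and the odd-month sentence was most likely written for stray visits during treatment. Section 8 and the V3.0 rationale promise data to Month 18, and several safety sections promise every protocol time point. This stands as an account of intent. It does not repair the wording: Table 2 windows Month 15 alongside the other visits, and no sentence exempts it.

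The reply also limits the harm, and here it stands in full. SAP 8.2.1 names treatment comparisons for BCVA at Months 6 and 12, section 8 carries Month 12 analyses to Month 18, and none is named at Month 15. What is at risk is descriptive tables in the CSR addendum. The data are still listed, with actual and analysis visit, and adverse event tables are not built by visit.

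On the gaps, the reply is that they reach only visits far outside the ± 6 or ± 14 day protocol windows, and that late Month 12 visits go to case review and are not discarded automatically. This too stands. What remains is that the review has no placement rule.

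A reader might infer three stronger things. The first is that the sponsor plans to exclude half the trial at Month 15. The documents show a wording conflict, not that intention. The second is that the odd-month rule alone halves the sham comparator from 80 to 40. The pooled column is also blocked by SAP 6.1, so correcting 6.3 by itself would not restore it. The third is that a known share of primary outcomes is lost in the gap. The documents give no count or rate of late Month 12 images.

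**Conclusion.** The point holds as a conflict inside the SAP. Applied literally, section 6.3 removes 120 of 240 planned subjects (96 to 102 under the plan's own loss assumption) from the Month 15 by-visit summaries of BCVA, LL-BCVA, IOP, eye examinations, vital signs, drug concentration and antibodies. Section 6.1 removes the pooled columns at the same visit. The primary endpoint is not affected by this part. The conclusion rests on taking the sentence at its word; the more sensible reading is probably what was meant, and the SAP should say so.

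The Table 2 gaps are real but secondary. They total 35 + 29 = 64 days and matter for the primary endpoint only if a Month 12 image was taken 16 to 50 days late. How often that happened cannot be judged from the documents.

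**What to change.** In SAP 6.3, state that the odd-month rule applies only to Months 1, 3, 5, 7, 9 and 11, and that Month 15 is summarized for all groups. In SAP 6.1, add Month 15 to the visits at which pooled sham and pooled APL-2 are shown. Confirm or correct the Month 15 lower limit of 412.

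For the gaps, keep Days 347 to 376 as the Month 12 window for the primary analysis. Write down a rule for visits on Days 377-411 and 482-510, and have it applied by staff masked to treatment. Include any such FAF images in a sensitivity analysis that models actual time since baseline. Because V3.0 was written after the 12-month results were seen (SAP 4.1 and 8.1.3), label that analysis as added afterwards.

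Two tempting repairs should be avoided. Extending Month 12 to Day 411 lets growth over up to 50 extra days count as 12-month growth. Wider windows in the EOM arms alone are also tempting, since an EOM treatment visit 15 or more days early, or a Month 2 to 10 visit 16 or more days late, falls in an odd month or, for an early Month 2 visit, may. But they would make the permitted timing differ by arm.

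The cost is a few sentences of SAP text, the table shells for one visit and one extra model. No new data are needed.
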